##### 13.1.3 Specimen processing

Each specimen should be processed as follows prior to shipping:

1. Allow the blood to clot for 30-60 minutes at room temperature.
2. Centrifuge the specimen for 15 minutes at 1,000 – 1,300 x g.
3. Remove the serum from the clot and place it into the provided polypropylene storage tube and label the tube.
4. A total minimum volume of 2 mL of serum is required to run the Platelia™ Aspergillus EIA and Fungitell® beta-D glucan assay.

##### 13.1.4 Storing specimens

1. Specimens should be frozen at -70°C the day of collection after following the above processing steps.
2. Specimens can be stored at -70°C until shipment. Specimens stored at -70°C may be stored indefinitely.

### 13.1.5 Shipping of specimens:

Each center will use shipping kits provided by MiraVista Diagnostics. These kits contain Styrofoam lined boxes, sealing tape, labels, and a cold pack. The boxes are designed to hold 10 frozen serum specimens. In order to optimize efficiency, a box should not be sent until 10 specimens have been collected.

#### Requisitions:

1. Complete an ACCL0933 GM & BG Requisition Form for each specimen sent for testing. All areas of the requisition form must be completed.

#### Packaging:

1. Assure all specimen labels and packaging labels are correct and legible. Please use the labels provided in the kits as they are designed to withstand specimen freezing and thawing without disruption of the written patient identification information. A Sharpie marker is most effective for writing on these labels.
2. Place the labeled vials containing the patient serum into a biohazard plastic bag along with absorbent material such as gauze or paper towel and seal. Use the biohazard plastic bags provided in the kit.
3. Ship specimens in the boxes provided along with the cold pack that should be frozen.
4. Open the box and remove the Styrofoam liner lid and the sealing tape.
5. Place the frozen cold pack into the liner. The frozen cold pack will ensure specimen integrity during overnight shipment.
6. Place the biohazard plastic bag containing the requisition forms and specimens directly on top of the frozen cold pack.
7. Replace the Styrofoam liner lid.
8. Complete an ACCL0933 GM & BG Requisition Form for each specimen and place them on top of the liner before sealing the box.
9. Wet the sealing tape provided in the kit and seal the cardboard box.
10. If the specimen tube labels and requisition forms do not match when received at MiraVista Diagnostics, a call will be made to the study site on the day of receipt.

### 13.1.6 Testing of specimens:

1. Testing of serum specimens for this study will be performed in batches.
  - a. Negative results are final.
  - b. Positive results are retested on the next work day for confirmation.
2. Testing will not occur under the following conditions:
  - a. The specimen has been stored under unacceptable storage times and/or temperatures.
  - b. The specimen has been shipped under unacceptable time and/or temperature conditions.
  - c. The specimen volume is less than needed to complete the testing process.
  - d. The specimen cannot be pipetted due to viscosity.
  - e. The specimen is hemolyzed or icteric for Fungitell®.
  - f. The specimen is of a type other than serum separated off the clot.
3. Platelia™ *Aspergillus* EIA results are reported as a GM index.
4. Fungitell® beta-D glucan assay results are reported as pg/mL.

### 13.1.8 Galactomannan and Beta-D glucan Assays

Testing will be performed by technicians blinded to each patient's clinical information. **Test results will not be made available to treating physicians since the utility of these tests is not yet established in children and because we will not be conducting testing in real time. Thus, results will not be utilized for clinical decision-making.**

To our knowledge BG testing is not routinely performed at many pediatric centers but may be performed at some of the COG sites while GM testing is currently performed at a number of pediatric centers. Regardless of the number of institutions offering such testing options, we anticipate that such testing will be ordered by a subset of treating physicians. The local BG and GM results will not be included in our final analysis of the 2 biomarker assays' operating characteristics. However, these results may effect a change from fungal prophylaxis to preemptive or empiric therapy and may encourage or discourage more comprehensive efforts to diagnose a proven or probable IFI in any given patient. This in turn may falsely influence our evaluation of the 2 biomarker assays' operating characteristics. For each patient we will identify whether local BG or GM testing has been performed and, via a sensitivity analysis, explore whether such a practice influences the operating characteristics. The plans for this sensitivity analysis are described in more detail in Section 13.8.4 below.

The Platelia *Aspergillus* EIA study is reported as a GM index. We will use the FDA-approved threshold of  $\geq 0.5$  GM index on a single test sample as our criteria for a positive test result. The Fungitell Assay is reported in pg per mL of patient's serum. The manufacturer recommendation for a single positive Fungitell assay result of  $\geq 80$  pg/mL will be used to define a positive test.

## 13.2 Background

### 13.2.1 Changing approach to antifungal therapy in pediatric AML patients

Various strategies for starting antifungal therapy in patients with cancer exist and include :

1. Prophylaxis: Initiation of antifungal therapy in asymptomatic patients without any evidence of IFI, during periods of high risk such as during prolonged neutropenia resulting from chemotherapy or bone marrow transplant.
2. Empirical antifungal therapy: Initiation or modification of antifungal therapy after persistence of fever in the setting of neutropenia and broad-spectrum antibiotics.
3. Preemptive therapy: Use of radiographic and/or specific biomarkers to identify and treat suspected IFI prior to overt clinical presentation.
4. Therapy for proven, probable or presumed IFI: Therapy initiated for the treatment of proven or probable IFI based on EORTC/MSG criteria or based on clinical presumption of IFI.

The significant morbidity and mortality associated with IFI among patients with AML has led many clinicians to adopt a strategy that includes antifungal prophylaxis during periods of neutropenia. Retrospective evaluation of neutropenic children receiving fungal prophylaxis with fluconazole or micafungin suggested a reduction in the risk for IFI. The ideal antifungal agent for such prophylaxis in children is not known and will be addressed in the primary aim of this study. Regardless of the specific antifungal agent, it is likely that prophylaxis will be successful and be integrated as the standard of care for all future pediatric AML therapy. Despite a reduction in IFI, prophylaxis will not eliminate all such infections. In patients with breakthrough infections on prophylactic therapy, early suspicion for IFI and modification of antifungal therapy will still be paramount to improving patient outcomes.

Unfortunately, the current approach for risk stratification of IFI (persistence of fever for  $\geq 5$  days on broad spectrum antibiotics) may be less than ideal in populations at high risk for IFI. The clinical presentation at the start of an IFI can range from completely asymptomatic, to fever without localizing signs or symptoms, to clinical sepsis. This is illustrated by a randomized trial of empiric caspofungin vs. liposomal amphotericin B. Patients were excluded from this study if they had a current documented IFI. Despite this, 4.9% of subjects were ultimately identified as having proven or probable IFI at baseline prior to initiating the antifungal treatment. Therefore, relying on traditional methods to guide empiric antifungal modifications would result in over-treating some patients with low likelihood of IFI and a failure to modify therapy in other patients that have an underlying IFI. A preemptive therapeutic approach that utilizes screening diagnostic studies to identify patients likely to have an IFI at the earliest possible point may be more rational and successful.

### 13.2.2 Traditional diagnostic studies to identify patients with suspected IFI

Traditional diagnostic modalities for IFI are limited to radiologic imaging and blood or tissue culture techniques. Radiologic studies may show visceral involvement but an invasive biopsy procedure is necessary to differentiate between a fungal or non-fungal infectious process. Although blood cultures may be used to isolate *Candida* spp. during candidemia, they are not helpful in the setting of invasive candidiasis without fungemia. Furthermore, traditional blood cultures are not typically successful at isolating mold infections such as *Aspergillus*. Cultures of tissue specimens can be definitive but require invasive techniques for sample procurement.

### 13.2.3 Galactomannan and Beta-D Glucan Assays

Alternative non-invasive approaches involve serial evaluation of a patient's serum for the presence of galactomannan (GM) or beta-D glucan (BG). The former is present in *Aspergillus spp.* while the latter is present in a vast majority of pathogenic fungi. Two validated FDA approved antigen detection assays, The Platelia *Aspergillus* EIA and the Fungitell Assay, currently exist for the detection of GM and BG, respectively.

#### 13.2.3.1 The Platelia *Aspergillus* EIA and Fungitell Assay in Adults

The Platelia *Aspergillus* EIA is a commercially available kit from Bio-Rad Laboratories that utilizes an EB-A2 monoclonal antibody and sandwich technique for detection of GM. In 2003, the assay received FDA approval for use in adults after it was prospectively validated in a cohort of immunosuppressed patients. This cohort included patients aged 16 years or older with various leukemias, lymphomas or those undergoing stem cell transplants. Twice a week testing was performed in 362 separate hospitalizations. Criteria for proven or probable invasive aspergillosis (IA) developed by the EORTC/MSG were used as the gold standard. This testing strategy resulted in 72.9% sensitivity, 94.7% specificity, 61.3% positive predictive value (PPV), and 96.8% negative predictive value (NPV) for detection of IA. Detection of GM preceded the time of definitive IA diagnosis in 96% of the proven IA cases by a median of 17 days. Two separate meta-analyses have since been performed which support the usefulness of GM screening in adults.

The Fungitell Assay (formerly Glucatell) is a commercially available kit from the Associates of Cape Cod, Inc. for the identification of BG in the serum of patients with IFI. This assay received FDA approval in May of 2004 to assist in the diagnosis of IFI. The operating characteristics of the assay have been elucidated in multiple adult cohorts. The first included adult patients with newly diagnosed AML or myelodysplastic syndrome undergoing initial Induction chemotherapy and receiving fungal prophylaxis with either caspofungin or itraconazole. The Fungitell Assay was performed in 283 patients twice a week for the duration of neutropenia resulting in sensitivity, specificity, PPV and NPV for diagnosing proven or probable IFI of 100%, 90%, 43%, and 100%, respectively. More importantly, a positive Fungitell Assay result was identified at a median of 10 days prior to the clinical diagnosis of IFI in this cohort.

The second study evaluated 95 adult patients with fever and neutropenia down to 16 years of age. Thirty-eight patients with proven, probable or possible IFI were identified. The resultant sensitivity, specificity, PPV and NPV were 97.4%, 28.6%, 55.2%, and 92.3% respectively. The specificity reported was reduced as compared to results from the prior publication as they included possible as well as probable and proven cases of IFI. Positive Fungitell Assay results preceded clinical diagnosis of IFI by a median of 5 days.

#### 13.2.3.2 The Platelia *Aspergillus* EIA and Fungitell Assay in Children

Multiple cohort studies have reported the operating characteristics of GM assay testing in pediatric patients undergoing therapy for acute leukemias or bone marrow transplantation (see Table 1). A number of these studies documented a 100% sensitivity of the GM assay including the study with the largest pediatric patient population. One study with fewer total patients did not reveal high sensitivity for GM assay testing but this study was limited as it only included one identified case of IA. None of these studies included patients on routine antifungal prophylaxis and thus the results cannot be extrapolated to our patient population.

Only one study evaluating BG levels in children has been performed. This study was limited to healthy children and revealed elevated baseline levels of BG in a subset of the patients. To date, the Fungitell Assay testing has never been performed in immunocompromised pediatric patients.

**Table 1.** Operating characteristics of Galactomannan testing for diagnosis of proven or probable aspergillosis in pediatric patients

Author, Year	Total # patients in study	Proven or probable aspergillosis	Sensitivity	Specificity	TP	FP	TN	FN
Steinbach, 2007	64	1	0%	87%	0	8	55	1
Hovi, 2007	89	1	100%	93%	1	6	82	0
Sulaihan, 2001	347	9	100%	89.9%	9	34	304	0
Rohrlich, 1996	37	10	100%	92.6%	10	2	25	0

#### 13.2.4 Gaps in knowledge

The Platelia *Aspergillus* EIA and the Fungitell Assay have each shown reassuring operating characteristics in adults making these biomarkers an attractive option for screening for IFI in children. More importantly, the 2 diagnostic tests afford the possibility of identifying an IFI days to weeks before the clinical diagnosis is made. However, it is not reasonable to extrapolate results from these adult studies to children. There is an absence of data regarding the operating characteristics of either biomarker in large homogeneous cohorts of children with leukemia.

Additionally, no data exist on either biomarker in a cohort of pediatric patients receiving antifungal prophylaxis. The use of prophylactic anti-fungal therapy will likely reduce the incidence of IFI or suppress actual IFI and thus potentially alter the predictive values of these biomarkers. As noted above, the use of prophylactic therapy will likely become standard of care and therefore it is imperative to define the operating characteristics of these biomarkers in such a population.

Lastly, it may be optimal to consider the results of each biomarker in combination as opposed to evaluating the impact of each study independently. **The simultaneous interpretation of both Platelia *Aspergillus* EIA and the Fungitell Assay for the identification of IFI in children has never been evaluated.** It is plausible that interpreting the 2 biomarkers in combination would improve the sensitivity of detecting an IFI.

#### 13.2.5 Summary

Currently, the decision to start empiric antifungal therapy in pediatric patients with neutropenia in the setting of AML is based on the persistence of fever despite a number of days of broad spectrum antibiotics. This approach is rudimentary and likely not particularly sensitive for the presence of an IFI. Maartens et al, identified afebrile and asymptomatic adults with IFI, emphasizing the need for better diagnostic studies and abandoning the use of persistent or new fever as the only trigger for antifungal modification. The availability of the Platelia *Aspergillus* EIA and the Fungitell Assay offer an opportunity to more accurately stratify pediatric patients for their risk for breakthrough IFI while on antifungal prophylaxis. Adult trial data for both of these assays are encouraging as they are almost always correct when the results are negative (i.e., high NPV) and maintain a reasonable sensitivity for presence of IFI (i.e., high sensitivity). Certainly, they may be at risk for false positive results (i.e., low PPV) which could result in unnecessarily treating patients without an IFI. Despite this potential for overtreatment it is still likely more desirable to have such results guide empiric antifungal decisions as opposed to the limited current practice of persistent fever and neutropenia.

However, before we can employ these biomarker assays as guides for initiating or escalating to empiric antifungal therapy in children we must better define their operating characteristics in the same population. The parent study cohort provides a one time opportunity to evaluate the operating characteristics of both of these tests in the setting of 2 different antifungal prophylaxis agents in a homogeneous cohort of pediatric AML patients. The choice of which antifungal agent to use for future trials will likely be

determined by the results of this study. Knowledge of the operating characteristics of each biomarker interpreted separately and in combination under these study conditions is necessary to inform their potential utility as integral markers to guide empiric antifungal choices for future AML patients.

### 13.3 Specific Aims

Primary Aim:

- i) To define the operating characteristics of 2 fungal antigen assays, Platelia *Aspergillus* EIA and Fungitell Assay for the identification of IA only and all IFI among pediatric AML patients receiving antifungal prophylaxis. This primary aim will have 3 sub-aims:
  - a) Define the test characteristics using a combination of the results from the Platelia *Aspergillus* EIA and Fungitell Assay for identifying IA only and all IFI.  
Hypothesis: A positive Platelia *Aspergillus* EIA **or** positive Fungitell Assay will be more sensitive at identifying patients with IA only or with IFI while on antifungal prophylaxis as compared to either test alone.
  - b) Define the test characteristics of the Fungitell Assay for identifying all IFI.  
Hypothesis: A single positive Fungitell Assay will have > 90% sensitivity in identifying all IFI in pediatric AML patients on antifungal prophylaxis.
  - c) Define the test characteristics of Platelia *Aspergillus* EIA for identifying IA only.  
Hypothesis: A single positive Platelia *Aspergillus* EIA will have > 90% sensitivity in identifying IA only in pediatric AML patients on antifungal prophylaxis.

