### 13.8 Statistical Design

#### 13.8.1 Sample Size and Estimated Event Rates

The parent trial comparing prophylaxis with caspofungin to fluconazole in newly diagnosed AML patients anticipates enrollment of at least 275 patients for each arm with a total cohort of approximately 550 patients. As noted above we anticipate that at least 80% of the patients enrolled in the parent trial will also be enrolled in this ancillary study. This will result in 220 patients from each study arm. Consent for testing will be included as a part of the parent trial enrollment, thus significantly limiting the need for additional resources to complete this biomarker study.

The estimated number of probable or proven IFI events for final analyses will be different for both proposed biomarkers as they account for different types of fungal infections and the incidence for each will vary by study arm. The Fungitell Assay has the potential to identify most pathogenic fungi and thus a majority of the probable or proven IFIs will be considered as true events (excluding IFIs from *Zygomycetes* and *Cryptococci*). The Platelia *Aspergillus* EIA is specific for *Aspergillus* and thus only probable or proven IA will be considered as true events for that analysis.

Based on Section 9.3.3 of the parent trial the estimated incidence of IFI for patients in the fluconazole group is 8% and 2% in the caspofungin arm. Assuming the enrollment of 220 patients in each study arm, there would 18 IFI events in the fluconazole group and 4 IFI events in the caspofungin group. Based on data from the CCG 2961 AML trial, one-third of microbiologically proven fungal infection were the result of *Aspergillus*. Therefore, it is estimated that 6 of the 18 IFI events in the fluconazole group will be IA and between 1 and 2 of the IFI events in the caspofungin group will be IA.

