#### 13.8.2 Sensitivity, Specificity, PPV, and NPV

The validity of a biomarker is based on whether the study appropriately categorizes patients with and without the illness in question (sensitivity and specificity). Alternatively the validity of a test can be measured by how well the test results predict the presence or absence of the disease (PPV and NPV). Collectively, sensitivity, specificity, PPV, and NPV are often referred to as the test's operating characteristics with the sensitivity and NPV being the most clinically relevant parameters for this study. Each component of the operating characteristics will be calculated based first on the entire cohort. As indicated in the sample size estimates above the incidence of IFI will vary between the two study arms. It is well documented that variations in the incidence/prevalence of a disease will impact the operating characteristics of a diagnostic test specifically for the PPV and NPV. Therefore, each assay's sensitivity, specificity, PPV and NPV will also be calculated separately for each study arm.

The operating characteristics for both the Platelia *Aspergillus* EIA and the Fungitell Assay will be computed at the patient level for each of the sub-aims as follows:

- a) Outcome of IA only **or** all IFI defined as a single positive test for either the Platelia *Aspergillus* EIA **or** the Fungitell Assay as compared to the EORTC/MSG criteria for proven or probable IA only **or** all IFI.
- b) Outcome of IA only defined as a single positive test for Platelia *Aspergillus* EIA only as compared to the EORTC/MSG criteria for proven or probable IA only.
- c) Outcome of all IFI defined as a single positive test for the Fungitell Assay as compared to the EORTC/MSG criteria for all proven or probable IFI.

Sensitivity, specificity, PPV and NPV and their accompanying 95% confidence intervals will be calculated using STATA statistical software version 11.0 (College Station, TX). As noted above, these parameters will first be calculated for the entire cohort and then for each study arm separately. The latter analyses are important as the incidence of IFI may vary by study arm thus impacting the interpretation of the assay results. A patient with multiple episodes of IFI will only be included in the analyses as a single IFI.

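### Sub-aim (a) hypothesises a sensitivity gain whose direction the either-positive rule guarantees, and no paired comparison on a common target is planned

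*Combined protocol and SAP*

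**What the plan says.** Section 13.2.4 presents joint interpretation of the two assays as an open question and thinks it plausible that "interpreting the 2 biomarkers in combination would improve the sensitivity of detecting an IFI". Section 13.3 turns this into the hypothesis for sub-aim (a): either assay positive "will be more sensitive at identifying patients with IA only or with IFI while on antifungal prophylaxis as compared to either test alone". It states no minimum gain and no condition on specificity. The other two sub-aims do set a bar, for example "A single positive Fungitell Assay will have > 90% sensitivity in identifying all IFI".

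Section 13.8.2 says that operating characteristics "will be computed at the patient level for each of the sub-aims as follows". The either-positive rule is assessed against IA and against all IFI, Platelia alone against IA only, and Fungitell alone against all IFI. (The single-assay items appear there in the reverse order of 13.3.) On method it says "Sensitivity, specificity, PPV and NPV and their accompanying 95% confidence intervals will be calculated using STATA", overall and by arm, "with the sensitivity and NPV being the most clinically relevant parameters for this study". No difference between the combination and a single assay is listed.

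**The concern.** The either-positive rule adds positives and removes none. In a common set of patients with one reference standard, it cannot be less sensitive or more specific than either component. Sub-aim (a) names only the measure that must hold or rise. Read as a statement about true sensitivities, it is correct unless one assay never finds a case that the other misses. Confirming it would say little about whether running both assays is worthwhile.

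The useful question is how many extra cases are found for how many extra false alarms. Separate intervals for each rule, computed in the same patients, do not give the uncertainty of that gain or loss. The comparison is also incomplete as listed: without Platelia for all IFI and Fungitell for IA, the rule cannot be set against both assays on the same target. Section 13.2.5 wants the combined results to inform future empiric antifungal choices, so an apparently confirmed hypothesis could be given more weight than it earns.

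**Working it through.** **1. Inputs.** Section 13.8.1 gives "This will result in 220 patients from each study arm" and "the estimated incidence of IFI for patients in the fluconazole group is 8% and 2% in the caspofungin arm".
- Cohort: 0.80 × 550 = 440.
- IFI: 220 × 0.08 = 17.6 (18) and 220 × 0.02 = 4.4 (4), which reproduces the plan's 18 and 4. The total is 22.
- IA at one third: 18/3 = 6 and 4/3 = 1.3, which reproduces the plan's 6 and 1 to 2. The total is 7 to 8.
- Without IFI: 440 − 22 = 418.

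The plan gives no power or sample-size figure for sub-aim (a), so there is none to reproduce.

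**2. Direction.** Among n diseased patients, let a be positive on both assays, b on Platelia only, c on Fungitell only and d on neither.
- Sensitivities: Platelia (a+b)/n, Fungitell (a+c)/n, either-positive (a+b+c)/n.
- Gain over Fungitell = b/n. Gain over Platelia = c/n. Neither can be negative.
- Listing every possible table for n = 7, 8 and 22 gives 120, 165 and 2,300 tables. None has the rule below a single assay. The rule ties with Fungitell (b = 0) in 36, 45 and 276 of them.

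The same layout in patients without disease shows that specificity can only tie or fall.

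**3. Specificity cost.** Section 13.2.3.1 cites adult specificities of 94.7% (Platelia) and 90% (Fungitell).
- Assuming independence: 0.947 × 0.90 = 0.852.
- Bounds without that assumption: 0.947 + 0.90 − 1 = 0.847, up to the smaller value, 0.90.
- Extra false positives over Fungitell alone: 418 × (0.900 − 0.8523) = 19.9, with bounds 0 to 418 × 0.053 = 22.
- With 89.9% for Platelia (largest paediatric study in Table 1): 418 × (0.900 − 0.899 × 0.90) = 38.
- With 85% for Fungitell (15% of healthy children at or above 80 pg/mL, Section 13.6.1.1) and 94.7% for Platelia: 418 × (0.850 − 0.947 × 0.85) = 19.

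**4. Sensitivity gain over Fungitell, all IFI.** Assume Fungitell sensitivity 90%, Platelia sensitivity for IA 72.9% to 90%, Platelia positivity in other IFI 0 to 5.3%, and independence.
- Low: 7 × 0.10 × 0.729 / 22 = 2.3 points.
- High: (8 × 0.10 × 0.90 + 14 × 0.10 × 0.053) / 22 = 3.6 points.

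This is less than one expected case (0.5 to 0.8).

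**5. Chance of an exact tie**, under the same assumptions about Platelia. P(tie with Fungitell) = [1 − (1 − sF) × sP]^(IA) × [1 − (1 − sF) × f]^(IFI − IA). Here sF is Fungitell sensitivity, sP is Platelia sensitivity for IA, and f is Platelia positivity in other IFI.
- sF 80%: 18% to 33%.
- sF 90%: 44% to 59%.
- sF 95%: 67% to 77%.
- sF 100%: certain.

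For IA, with Fungitell sensitivity 80% to 100%, P(tie with Platelia) is 8% to 18% at Platelia sensitivity 72.9% and 43% to 56% at 90%.

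**6. Precision.** Each gain is a simple proportion, so an exact binomial interval applies.
- 0 of 22 extra cases: 0 to 15 points.
- 1 of 22: 4.5 points, interval 0.1 to 23.
- 1 of 8 IA: 12.5 points, interval 0.3 to 53.
- A specificity loss of 20/418 = 4.8 points has a normal-approximation interval of ± 1.96 × √(0.048 × 0.952 / 418) = ± 2.0 points.

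An exact paired test would need six extra cases for two-sided p < 0.05 (2 × 0.5⁶ = 0.031; five give 0.0625). With 8 IA, Platelia sensitivity 90% and Fungitell sensitivity 80% to 90%, the chance of six or more is below 0.1%. Because discordance in cases runs one way by construction, such a p-value would mean little anyway.

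**The case against.** A reader might infer that the hypothesis can never be contradicted. The documents do not support that. The wording is strict, so a tie fails it. Ties are likely at these event counts (step 5), and a tie is certain for all IFI if Fungitell reaches the 100% sensitivity cited from adults in Section 13.2.3.1. Only a reversal is ruled out.

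Even that guarantee is conditional on common patients and a common target. Section 13.1.6 rejects haemolysed or icteric specimens for Fungitell only, and Section 13.8.2 uses different targets for the single assays. A loose comparison could show the rule with the lower figure.

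A reader might also infer that the trial cannot learn whether combining the assays helps. That goes too far. Sub-aim (a) is itself framed as defining test characteristics, and specificity, PPV and NPV with intervals are planned for the rule and for each assay. The trade-off is acknowledged: Section 13.6.1.1 knowingly favours sensitivity and NPV, and Section 13.2.5 discusses overtreatment. For all IFI, the point differences from Fungitell can be read from the planned output, as can those from Platelia for IA.

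Finally, with so few events a paired analysis will be imprecise, and this is an optional ancillary study whose results are not returned to clinicians (Section 13.1.8).

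All of this stands. It does not supply the missing paired differences or the two missing assay-by-target estimates, and it does not make the hypothesis informative. The plan also lets specificity override sensitivity elsewhere: Section 13.6.1.1 rejects a 60 pg/mL cut-off because of false positives. The either-positive rule gets no such check.

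**Conclusion.** The point holds as a minor one about wording and analysis. On common patients and a common target, the hypothesis can end only in a gain or a tie, and it leaves out the measure that can only tie or worsen. The planned outputs do not estimate the trade-off with its uncertainty, and they do not cover both assays on both targets.

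On the protocol's cited adult specificities, the rule would produce about 20 more false positives than Fungitell alone among 418 patients, for an expected gain of 2 to 4 points in 22 IFI if Fungitell sensitivity is 90%. The direction and the specificity bounds need no independence assumption; the central figures do. They also carry adult values into children followed over up to four courses, which may not transfer. The trial's primary comparison is unaffected.

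**What to change.** Reword sub-aim (a) as estimation and add a paragraph to Section 13.8.2:
- Define the set of patients evaluable on both assays.
- For each target (IA; all IFI), report the paired gain in sensitivity and the paired loss in specificity of the either-positive rule against each single assay, with 95% confidence intervals. Compare with both assays, not with whichever looks better in the data, because that choice adds selection bias.
- Give the counts of extra true positives and extra false positives beside these differences.
- Base any conclusion on gain and loss together, and make no significance claim.

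The cost is wording and one extra table from data already to be collected. The downside is wide intervals for the sensitivity gain with about 22 IFI and 7 to 8 IA, which the text should state in advance.
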